15.5 Analysis of Correlative Science Endpoints

The relevant background, objectives and methodologies for the correlative studies are described in section 13, and statistical considerations relevant to these endpoints are considered here.

15.5.1 Proteomic studies

We will compare changes in the levels of specific total and phosphorylated proteins from

baseline tumor samples to samples obtained during cycle 1 week 2 of treatment with the study agent in a subset of 10 liposarcoma patients. This endpoint is analyzed with exploratory intent given the limited sample size, as we expect to obtain tumor tissue from only approximately 10 patients enrolled in the study. Spot intensity data from the RPPA platform are normalized prior to reporting. The RPPA technology is described in detail in section 13. If the data are normally distributed, a paired t-test will be employed to evaluate whether differences between the baseline and on-treatment spot intensity differ from zero for each protein studied. If the data are not normally distributed, the Wilcoxon-signed rank test will be used.

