2.3 Correlative Science Objectives

- 2.3.1 To use reverse phase proteomic arrays (RPPA) to evaluate changes in total and phosphorylated MGCD516 target RTK expression in tumor specimens from a subset of liposarcoma patients at baseline and while on treatment with the study agent to confirm evidence of on-target effects and evaluate potential predictive biomarkers.
- 2.3.2 To use next generation sequencing techniques to evaluate pre-treatment tumor biopsies from liposarcoma patients for a defined set of genetic alterations involving MGCD516 targets, and to assess the relationship between the presence of such genetic alterations and clinical efficacy.

For details on the reporting of the endpoints, see section 15, Statistical Considerations.

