13.1 Proteomics studies

Introduction

Reverse phase protein array (RPPA) is a functional proteomics technology capable of profiling protein levels and post-translational modifications, including phosphorylation, across various biological specimens, including human tissue, using a miniaturized analyte-down dot-blot immunoassay. The technique allows for monitoring of protein expression across a large number of samples in a quantitative, high-throughput and cost-effective manner not currently matched by other proteomics technologies.

In RPPA, analytes are immobilized on a solid phase, most often nitrocellulose, and probed with an affinity reagent, usually a high-affinity validated antibody. The technology is particularly well suited for profiling the state of cell signaling networks owing to small sample requirements, high sensitivity in the picomolar range and precision as demonstrated by coefficient of variance < 15%. RPPA has been used in a range of preclinical and clinic research applications for identification of novel therapeutic targets and predictive biomarkers, pharmacodynamic analysis and monitoring of therapeutic response.²⁷

We aim to employ RPPA to analyze changes in total and phosphoprotein RTKs between baseline and on-treatment tumor biopsy specimens in order to demonstrate pharmacodynamic evidence of on-target activity by MGCD516, evaluate drug effects on activation/suppression of downstream signaling pathway components and assess for possible compensatory upregulation of alternative RTKs and signaling pathway components as a mechanism of acquired resistance. Specifically, we will study changes in total and phosphoprotein levels for the following proteins: 4E-BP1, Akt, AXL, EGFR, Eph family, ERK 1/2, FGFR2, IGF1-R, KIT, MEK 1/2, MET, p70 S6 kinase, RET, RYK, PDGFRa, PDGFRb and VEGFR1-2. Significant changes in total and phosphoRTKs will then be confirmed by Western Blot.

Prior Clinical Studies Employing RPPA

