The following procedures and analysis will be performed by Theralink Technologies, Inc.. Sections are analyzed for adequacy by a pathologist and specimens with predominant necrosis or lymphocytic infiltration are not used. Tumor cells and/or stromal cells are microdissected using an Arcturus PixCell IIe (Invitrogen, Life Technologies, Grand Island, NY). Microdissected cells are stored at -80C prior to reverse phase protein microarray printing. Microdissected cells are subject to lysis with a 10% (v/v) solution of Tris(2-carboxyethyl) phosphine (Pierce, Rockford, IL) or a 2.5% solution of 2- mercaptioethanol (Sigma) in Tissue Protein Extraction Reagent (T-PERTM, Pierce)/Tris-glycine 2X SDS buffer (Invitrogen). Cell lysates are stored at -80C prior to microarray construction.

Cellular lysates are printed on glass backed nitrocellulose array slides (FAST Slides, Whatman,

Florham Park, NJ) using an Aushon 2470 arrayer (Aushon BioSystems, Burlington, MA) equipped with 350-µm pins. Each array consists of microdissected tumor samples. The before/after pair for each patient are printed on the same array for most specimens. Samples are printed in duplicate in 4-point or 2-point dilution curves. Immunostaining is performed on a Dako Autostainer per manufacturer's instructions (CSA kit, Dako, Carpinteria, CA). Each slide is incubated with a single primary antibody at room temperature for 30 minutes. Reverse phase protein microarray analysis of phosphorylated/total protein endpoints is then conducted for the RTK targets described in section 13.1.1. Antibodies were validated by Western blotting. The negative control slide is incubated with antibody diluent as a substitute for the primary antibody. Secondary antibody is goat anti-rabbit IgG H+L (1:7,500) (Vector Labs, Burlingame, CA) or rabbit antimouse IgG (1:10) (Dako). Subsequent signal detection is amplified via horseradish peroxidase mediated biotinyl tyramide deposition with chromogenic detection per manufacturer's instructions (Dako). Array slides are scanned at 600dpi on a flatbed scanner (UMAX PowerLook) and saved in a tiff format (Adobe Photoshop). Spot intensity is analyzed using ImageQuant ver 5.2 (GE Healthcare). Total protein per microarray spot is determined with a Sypro Ruby protein stain (Invitrogen/Molecular Probes) per manufacturer's directions and imaged with a CCD camera (NovaRay, Alpha Innotech, San Leandro, CA).

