Data compilation is performed with proprietary software for background correction and normalization. The mean local area background of each spot is used to assess spot intensity values greater than 2 S.D. above background. Replicate values are averaged. If the CV between replicates is >20%, the spot is flagged and a value of "CV too high" reported. Signal intensity from the secondary antibody alone (negative control) slide is subtracted from the signal intensity of the primary antibody slide. Each patient analyte sample is normalized to the corresponding Beta actin value. Total protein is analyzed as a quality control marker for each microarray spot. Total protein per spot is quantified as a means to assess overall sample and printing quality. Low total protein levels indicate inadequate sample quality or quantity. The results of the analysis will be reported to the study coordinators at CUMC along with the patient's identification number and date of birth and subsequently will be added to the case report form and appropriate files. Unused tissue will be returned by Theralink Technologies, Inc. to the institution which performed the procedure to obtain them.

Western Blot Procedures:

These studies will be performed in the laboratory of [name] at CUMC. We will attempt to confirm RPPA findings by assessing changes in total and phosphorylated MET, IGF1-R and PDGFRb (RTKs identified as important for LPS proliferation in preclinical studies) by Western blot in the pre-treatment and post-treatment tumor biopsy specimens. Assessment of these targets in pre-treatment biopsies will also serve to evaluate whether phosphorylated expression of these targets demonstrated in cell lines is recapitulated in human tissue. We will also use Western blot to validate changes in other RTKs in which significant changes were identified by the RPPA analysis if available tissue permits. Briefly, protein extractions are prepared using a radio immunoprecipitation assay lysis buffer. Protein concentrations are measured using the BioRad protein assay and equal amounts loaded onto gradient gels. Membranes are probed with primary antibodies and bound antibodies are then detected with horseradish peroxidase and visualized by enhanced chemiluminescence reagents. Validated

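### Section 15.5.1 tests total and phosphorylated protein separately, with no phospho-to-total ratio or joint rule, so on-target inhibition is not separated from a change in receptor amount

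*Combined protocol and SAP*

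**What the plan says.** Objective 2.3.1 is to "evaluate changes in total and phosphorylated MGCD516 target RTK expression in tumor specimens", in part "to confirm evidence of on-target effects". Section 13.1 states the same purpose for the paired biopsies: to "demonstrate pharmacodynamic evidence of on-target activity by MGCD516".

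Section 15.5.1 compares "changes in the levels of specific total and phosphorylated proteins" in about 10 liposarcoma patients. It uses a paired t-test, or the Wilcoxon signed-rank test if the data are not normal, to "evaluate whether differences between the baseline and on-treatment spot intensity differ from zero for each protein studied". It describes the analysis as exploratory and gives no alpha, effect size or variance.

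On normalization, section 13.1 says: "Each patient analyte sample is normalized to the corresponding Beta actin value". The laboratory description adds: "Reverse phase protein microarray analysis of phosphorylated/total protein endpoints is then conducted for the RTK targets". The slash is not defined as a quotient, and section 15.5.1 does not take up a ratio. The Western blot work in 13.1 also covers both forms, again without combining them.

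**The concern.** For a kinase inhibitor, direct evidence of target inhibition is a fall in the share of receptor that is phosphorylated. The phospho signal is the product of two things: how much receptor there is, and what share of it is phosphorylated. A test of phospho level against zero change responds to both. Beta-actin normalization corrects for how much cell material was loaded, not for how much receptor those cells carry.

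The planned test of total protein shows whether receptor amount moved. It does not show whether phosphorylation per receptor moved as well. The plan has no ratio, no adjustment of the phospho change for the total change, and no rule for which pattern of results counts as inhibition. At stake is how clearly the paired core biopsies can answer the question they are taken for. If the ratio is chosen only after the data are seen, any on-target statement based on it is post hoc.

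**Working it through.** The documents state no power or effect size for the proteomic tests, so there is no figure of the plan's to reproduce. What follows illustrates the mechanism.

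**Inputs**
- 10 pairs: sections 13.1 and 15.5.1.
- Assay SD a = 0.15 per measurement on the log scale: taken from the coefficient of variation below 15% that 13.1 gives for RPPA in general.
- Assumed, not in the documents: two-sided 5% level; SD of the within-patient log change 0.3, 0.4 or 0.5, both for total receptor (sT) and for phosphorylated share (sF); total and share changing independently; the effect sizes below.

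**Model.** Change in log phospho = change in log total + change in log share. Each observed change carries assay error with variance 2a².

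- Var(phospho change) = sT² + sF² + 2a²
- Var(total change) = sT² + 2a²
- Var(log ratio change) = sF² + 4a²; the true change in total cancels

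**Hand check at sT = sF = 0.4**
- Total down 30%: ln 0.7 = −0.357; SD = √(0.16 + 0.045) = 0.453; standardized effect 0.79. A paired t-test with 10 pairs has power 0.616 at 0.8, in line with the simulated 60%.
- Share down 40%, ratio test: ln 0.6 = −0.511; SD = √(0.16 + 0.09) = 0.50; standardized effect 1.02. Power is 0.803 at 1.0, in line with the simulated 82%.

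**Simulated results** (% of trials, at SD 0.3 / 0.4 / 0.5)

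| Truth | Pattern from the two planned tests | Frequency of pattern | Ratio test rejects |
|---|---|---|---|
| Receptor −30%, no inhibition | phospho down and total down | 50 / 31 / 21 | about 5 |
| Receptor −30%, share −40% | phospho down and total down | 78 / 60 / 45 | 92 / 82 / 70 |
| Receptor +50%, no inhibition | total up, phospho not significant | 25 / 30 / 28 | about 5 |
| Receptor +50%, share −40% | total up, phospho not significant | 80 / 68 / 54 | 92 / 82 / 70 |

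In each pair of rows the same combination of planned results is common with and without inhibition. The ratio test separates the two cases, because receptor amount drops out of it.

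**When the ratio costs power.** It has the larger variance when 4a² exceeds sT² + 2a², that is when sT is below √(2 × 0.15²) = 0.21. Example: total unchanged on average, sT = 0.1, sF = 0.4, share down 40%. The phospho SD is √(0.01 + 0.16 + 0.045) = 0.464 and its standardized effect 0.511/0.464 = 1.10. The ratio SD is 0.50 and its effect 1.02. Power falls from about 0.87 to 0.82. With sT = sF = 0.3 to 0.5 and total unchanged on average, the ratio does better: 70-92% against 50-86% for phospho.

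**The case against.** The strongest reply is that the plan does test total protein, so a reader will see receptor change. That is correct, and it rules out a tempting stronger reading: that phospho level is tested alone and a phospho drop will be taken as inhibition. No section says so. The simulated 28-56% rejection rate of the phospho test with no inhibition and receptor down 30% applies only to someone who ignores the total result. The plainly misleading pattern, phospho down with total not significant, occurs in about 7% of those trials. With a twofold fall in receptor (SD of log2 change 0.5 to 1.0, assay error SD 0.25 on each change), the total test flags it in 78-99.9% of trials.

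That reply does not close the matter. Knowing that receptor amount changed does not show whether phosphorylation per receptor changed, as the table demonstrates.

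Other points that stand:
- The aim in 13.1 to "assess for possible compensatory upregulation of alternative RTKs and signaling pathway components" concerns alternative receptors. A reader might infer that the protocol expects the inhibited receptor itself to rise; the text does not say that.
- Section 13.1 also measures downstream proteins such as Akt and ERK 1/2, so the on-target reading need not rest on one receptor result.
- The phosphorylated/total wording in 13.1 could have been meant as a ratio. If so, 15.5.1 should say so.
- The variances, effect sizes and independence are assumptions. The ratio result does not depend on independence of total and share, because total cancels; the results of the separate phospho test do.
- The analysis is exploratory, and the ratio can be computed later from the same data. That keeps severity low, but it does not make a later choice prespecified.

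**Conclusion.** The point holds in a limited form. Both forms of each protein are tested, but separately and normalized only to actin. With no ratio or joint rule prespecified, the on-target objective in 2.3.1 and 13.1 is not separated from change in receptor amount, even when the two results are read together. Under the assumed SDs and a 30% receptor loss, both forms fall significantly in about 21-50% of trials with no inhibition and 45-78% with a 40% inhibition. The ratio test rejects in about 5% and 70-92%. These figures illustrate the mechanism and do not predict this trial's results. Severity is low: about 10 patients, an exploratory correlative endpoint, and no bearing on the primary endpoint or the Simon decision.

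**What to change.** In section 15.5.1, for each receptor tyrosine kinase with both forms measured, add the within-patient change in log(phospho/total) as the prespecified test of on-target inhibition, with both forms actin-normalized as planned. Keep the planned tests of total and phosphorylated change and report them alongside: total shows up- or downregulation, and phospho shows the net signal. State in 13.1 whether the phosphorylated/total wording means this ratio.

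The cost is wording only, with no new tissue or assay. The ratio carries the assay noise of two measurements, so power drops slightly (about 0.87 to 0.82 in the example above) if total receptor hardly varies. A pair in which either form is unusable, for example flagged for high replicate variation under 13.1, also drops out of the ratio test.

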15.5.2 Genomic studies

We will conduct next generation sequencing in all baseline tumor tissue from all liposarcoma patients (when sufficient material exists) to assess for a set of predefined genetic alterations in known targets of MGCD516. The genetic status of the tumor will then be considered on a binary basis; that is, a patient tumor specimen either has or does not have one of the predefined genetic alterations. We will then assess for a relationship between the presence of a genetic alteration with clinical outcomes. For tumor response, the two groups will be compared using Fisher's exact test given the small sample sizes. Progression free and overall survival will be compared between the two groups by a log-rank test.

15.6 Reporting and Exclusions

15.6.1 Evaluation of toxicity

The safety population will consist of all patients who received at least one dose of study drug.

15.6.2 Evaluation of response

All patients included in the study who receive at least one treatment with the study drug will be assessed for response to treatment, even if there are major protocol deviations or if they are ultimately deemed ineligible. Each patient will be assigned one of the following categories: 1) complete response, 2) partial response, 3) stable disease, 4) progressive disease, 5) early death from malignant disease, 6) early death from toxicity, 7) early death from other cause, or 9) unknown (not assessable or insufficient data).

All of the patients who met the eligibility criteria, with the exception of those who received no study medication, will be included in the main analysis of the response rate. Patients in response categories 4-9 are considered to have a treatment failure. An incorrect treatment schedule or drug administration does not result in exclusion from the analysis of the response rate.

15.6.3 Reporting of endpoints if study proceeds to exploratory cohort

If the study fails to meet the stage I endpoint in liposarcoma and proceeds to enroll the exploratory cohort, the primary endpoint (progression free rate at 12 weeks) and secondary efficacy endpoints (overall survival, progression free survival, response rate) will be reported separately for the liposarcoma population and the exploratory cohort population. The individual

best response of the patients in the exploratory cohort will be reported individually. The adverse event data will be reported in aggregate for the entire study population.

16. PROTECTION OF HUMAN SUBJECTS

This study is to be conducted in accordance with applicable government regulations and Institutional research policies and procedures.

This protocol and any amendments will be submitted to a properly constituted Institutional Review Board (IRB), in agreement with local legal prescriptions, for formal approval of the study conduct. The decision of the IRB concerning the conduct of the study will be made in writing to the investigator and a copy of this decision will be obtained before commencement of this study.

All subjects for this study will be provided a consent form describing this study and providing sufficient information for subjects to make an informed decision about their participation in this study. This consent form will be submitted with the protocol for review and approval by the IRB for the study. The formal consent of a subject, using the IRB-approved consent form, must be obtained before that subject is submitted to any study procedure. This consent form must be signed by the subject or legally acceptable surrogate, as outlined in the IRB approved protocol, and the investigator-designated research professional obtaining the consent.

17. STUDY FINANCES

17.1 Conflict of Interest

Any investigator who has a conflict of interest with this study (patent ownership, royalties, or financial gain greater than the minimum allowable by their institution, etc.) must have the conflict reviewed by the Columbia University Conflict of Interest Committee with a Committee-sanctioned conflict management plan that has been reviewed and approved prior to participation in this study. All CUMC investigators will follow the University conflict of interest policy.

17.2 Subject Stipends or Payments

No stipends or payments will be given to subjects.

18. PUBLICATION PLAN

Neither the complete nor any part of the results of the study carried out under this protocol, nor any of the information provided by the sponsor for the purposes of performing the study, will be published or passed on to any third party without the consent of the study sponsor. Any investigator involved with this study is obligated to provide the sponsor with complete test results and all data derived from the study.

19. GUIDELINES FOR AFFILIATE INSTITUTIONS IN MULTICENTER STUDIES

19.1 Multi-site Communication

The CPDM Office at CUMC provides administration, data management, and organizational support for the affiliate sites in the conduct of a multicenter clinical trial. The CPDM Office will coordinate regularly scheduled conference calls with affiliate sites.

The following issues will be discussed, as appropriate:

- Enrollment information
- Cohort updates (e.g., DLTs)
- Adverse events (e.g., new adverse events and updates on unresolved adverse events and new safety information)
- Protocol violations
- Other issues affecting the conduct of the study

19.2 New Protocol Distribution, IRB Submission, Modifications, Renewals

- Protocol specific documents are distributed to affiliate sites once CUMC IRB approval has been obtained.
- The affiliate site must submit a draft of site specific revisions to protocol and/or consent form documents for review and approval by the sponsor-investigator prior to submission to the local IRB. Draft documents should be sent to the study specific email address. The site will be provided confirmation that they are approved to submit to their local IRB.
- Protocol amendments must be approved by the affiliate site's local IRB within 90 days of distribution to the site by the sponsor-investigator.

19.3 Regulatory Documents

Prior to Site Initiation, the Sponsor-Investigator will ensure that proper requests are made of sites and that the following documentation is collected, prior to the initiation of an affiliate site.

- CV of PI, Co-I's and other research staff listed on FDA 1572 (signed and dated copy within 2 years)
- Medical Licenses of PI and Co-I's (current copy)
- Human subjects training certificates for PI and Co-I's
- CLIA/Laboratory Certifications for Local Laboratories listed on FDA 1572
- Local Laboratory Director's CV and License
- Local Laboratory Reference Ranges
- IRB roster or statement of compliance
- FDA Form 1572, if applicable (wet ink originals required)
- Financial Disclosure forms for all members listed on FDA 1572 (wet ink originals required)

Ongoing Regulatory Documentation: Sponsor-Investigator will ensure that proper requests are made of sites and that the following documentation is collected throughout the course of the study.

- IRB approval letters for all protocol modifications and all renewals
- IRB-approved consent forms
- Current IRB roster, if statement of compliance is not provided as part of site initiation
- FDA Form 1572, if applicable as updates are required
- Updated investigator and site information where relevant (e.g., CV, medical licensure and Financial Disclosure for new sub-investigator, local laboratory information)

Regulatory documents may be sent to [contact] or to the following address if wet ink originals are required:

Clinical Protocol & Data Management Office [name]

